17.2.1 Recording Adverse Events

The staff will record all AEs observed, queried, or spontaneously volunteered by the subjects (regardless of seriousness or relationship to study treatment) in the appropriate section of the subject’s case report form or source documents. Subjects experiencing AEs (including those withdrawn from the study due to an AE) will be followed until recovery to a satisfactory state, or stabilization, or appropriate outcome is established as judged by the Investigator. Exacerbation of conditions related to the signs and symptoms of Dry Eye will not be reported as an AE.

The following details will be recorded for AEs:

- Description of event/symptom
- Onset date and time of event
- End date and time of event
- Maximum severity/intensity rated as follows:
 - Mild: Causing no limitation of usual activities, the subject may experience slight discomfort.
 - Moderate: Causing some limitation of usual activities, the subject may experience annoying discomfort
 - Severe: Causing inability to carry out usual activities, the subject may experience intolerable discomfort or pain
- Action taken with study treatment noted as follows:
 - Dose not changed

- Dose reduced
 - Drug interrupted
 - Drug withdrawn
 - Not applicable
 - Unknown
- Any other action taken (such as concomitant medication, non-drug therapy, hospitalization or none)
- Outcome of AE noted as follows:
 - Fatal
 - Not recovered/not resolved
 - Recovered/resolved
 - Recovered/Resolved with sequelae
 - Unknown
- Causality noted as follows:

Related:	A causal relationship between the study treatment and the AE is a reasonable possibility.
Not Related:	A causal relationship between the study treatment and the AE is not a reasonable possibility.

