5. STUDY SCHEMATIC

Table 5.1-1: Schedule of Assessments

Procedure	Visit 1 Day -21 to -8 Screening/Baseline	Visit 2 Day 1 + 2 Randomization/ Dry Eye Chamber	Visit 3 Day 8 + 2 Dry Eye Chamber
COVID-19 screening questionnaire, oral temperature and COVID-19 rapid test	X	X	X
Informed Consent	X		
Demographics	X		
Medical/Medication & Ocular History	X		
Medical/Medication Update		X	X
Urine Pregnancy Test (for all female subjects)	X	X	X
Dry Eye Chamber ¹	X	X	X
Symptom Questionnaires (Ocular Discomfort Score/Ocular Itching Score) ²	X	X	X
Inclusion/Exclusion Criteria Review	X	X	X
Snellen Visual Acuity ³	X	X	X
Slit-lamp Examination ³	X	X	X
Saline Instillation	X		
Intraocular Pressure (IOP)	X ⁴		
Dilated Fundoscopy	X ⁵		X ⁵
Randomization		X	
Test Article Instillation		X	X
Adverse Event /Concomitant Medication Query	X	X	X
Study Exit			X

¹Dry eye chamber exposure (approximately 45 minutes).

²Will be performed within approximately 15 minutes prior to the entry and every 5+2 minutes while in the chamber.

³Will be performed pre-chamber (prior to symptom questionnaires) and post-dry eye chamber.

⁴Will be performed prior to dry eye chamber entry. These tests will be performed prior to symptom questionnaires.

⁵Will be performed post-DEC after SVA and SLE

Note:

- 1. A washout period of at least 7 days following visits 1 and 2 is given in this study.
- 2. [REDACTED] training will be provided to the study participants at Visit 1, 2 and 3.

Table 5.1-2: Schedule of Subject Assessed Ocular Discomfort/Ocular Itching

Time points in minutes	0	5	10	15	20	25	30	35	40	45
Window (minutes)	-15	+2								
Visit 1, 2 and 3	X	X	X	X	X	X	X	X	X	X

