5.1 Endpoints

5.1.1 Exploratory Endpoints

- Change in ocular discomfort score (0-10) from baseline over 45 minutes in the dry eye chamber
- Change in ocular itching score (0-10) from baseline over 45 minutes in the dry eye chamber

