5.1.2 Safety Endpoints

The safety endpoints are as follows:

- Snellen visual acuity (SVA)
- Slit-lamp examination (SLE)
- Adverse event (AE) query

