11.2 Visit 1: Screening (Day -21 to -8)

The following activities will be completed at Visit 1:

- Subjects will be asked to sign and date the Informed Consent Form.
- Demographic data, including date of birth, age, race and ethnicity, will be recorded.
- Medical/Medication and Ocular history will be completed for each subject.
- A urine pregnancy test will be performed (for all female subjects). Subjects with a positive result will be excluded.
- The subjects will be evaluated for study inclusion, exclusion and restriction criteria.
- Symptom Questionnaires (Ocular Discomfort Score, Ocular Itching Score) will be performed within 15 minutes prior to DEC entry and every 5 +2 minutes up to 45 minutes while in the chamber.
- An SVA and SLE will be performed pre and post-DEC.
- IOP will be performed prior to DEC entry and dilated funduscopy will be performed post-DEC.
- Saline will be administered in the clinic approximately 5 minutes prior to the DEC entry.
- DEC session (approximately 45 minutes).
- Adverse events and concomitant medications will be recorded before the subject leaves the site.
- After 7 ± 1 day of washout period, eligible subjects will come to Visit 2

11.3 Visits 2 (Day 1 + 2) and 3 (Day 8 + 2): Treatment/Dry Eye Chamber

Eligible subjects will return for 2 treatment visits. The treatment visits will occur following at least 7 days after visits 1 and 2. At Visit 2 the subjects will be randomized to receive one of the 2 treatment sequences as mentioned in [Section 10.2](#). At Visits 2 and 3, the following activities will be performed:

- Medical/medication and ocular history will be updated for each subject.
- A urine pregnancy test will be performed (for all female subjects). Subjects with a positive result will be excluded.
- The subjects will be evaluated for study inclusion, exclusion and restriction criteria.
- An SVA and SLE will be performed pre and post-DEC.
- Symptom questionnaires (Ocular Discomfort Score, Ocular Itching Score) will be performed within 15 minutes prior to study treatment administration and approximately every 5 minutes while in the chamber.
- Test product will be administered in the clinic approximately 5 minutes prior to the DEC entry.
- DEC session (approximately 45 minutes).
- Dilated funduscopy will be performed post-DEC after SVA and SLE at Visit 3.
- Adverse events and concomitants medications will be recorded before the subject leaves the site.
- Study exit (Visit 3).

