12. STUDY ASSESSMENTS AND PROCEDURES

12.1 Efficacy Assessments

12.1.1 Ocular Discomfort Score and Ocular Itching Score

Ocular discomfort score and ocular itching score will be measured within 15 minutes before chamber entry and over 45 minutes (every 5 minutes) in the DEC. The ocular discomfort score is a participant-reported symptom index (0 to 10 scale; 0 represents no discomfort, 10 represents maximum discomfort). Ocular itching score is a participant-reported symptom index (0 to 10 scale; 0 represents no itching, 10 represents maximum itching). The assessments of ophthalmic signs and symptoms will be self-administered by subjects using an electronic P [REDACTED].

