14.2 Safety Analysis

Safety analysis will include descriptive analysis and listings according to received treatment. Safety analysis will be performed on all subjects receiving at least one dose of study medication. Subject's safety data will be presented according to the treatment they actually received. The Safety population will be used for all analyses of safety endpoints as well as demographics and baseline characteristics.

Adverse events and SAE will be classified using standard Medical Dictionary for Regulatory Activities (MedDRA) terminology Version 23.1 and presented by the treatment group. Summary tables listing the type, date of onset, date and time of resolution, incidence, severity, outcome, action taken, and Investigator's opinion of relationship to the study product will be presented by treatment group for AEs reported after randomization.

Concomitant medication used during the study will be listed by treatment and subject.

14.3 Interim Analyses No interim analysis is planned at this point.

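### The protocol's sections disagree on whether the Visit 2 and 3 pre-chamber score precedes the drop, and the dry eye AE exclusion has no exception for drop reactions

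*Combined protocol and SAP*

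**What the plan says.** **Timing of the pre-chamber score.** Both products are given about 5 minutes before chamber entry (Sections 8.1 and 10.1). For Visits 2 and 3, Section 11.3 sets the symptom questionnaires "within 15 minutes prior to study treatment administration and approximately every 5 minutes while in the chamber", and the synopsis (Section 4, Study Conduct II) also puts the first one before the dose. Section 12.1.1 says instead that the scores "will be measured within 15 minutes before chamber entry and over 45 minutes (every 5 minutes) in the DEC". Footnote 2 of Table 5.1-1 uses the same entry anchor. So does Table 5.1-2, "Schedule of Subject Assessed Ocular Discomfort/Ocular Itching", which gives time 0 a window of -15 for all three visits. Visit 1 has the same split: the synopsis counts back from the saline drop, Section 11.2 from chamber entry.

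**Endpoint.** Section 5.1.1 defines "Change in ocular discomfort score (0-10) from baseline over 45 minutes in the dry eye chamber", with a matching itching endpoint. Neither says which score is the baseline. Table 5.1-1 heads the Visit 1 column Screening/Baseline.

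**Adverse events.** Section 5.1.2 lists "Adverse event (AE) query" as a safety endpoint. Section 17.2.1 has staff record all AEs "regardless of seriousness or relationship to study treatment" and then adds: "Exacerbation of conditions related to the signs and symptoms of Dry Eye will not be reported as an AE". Section 14.2 lists the contents of the AE tables and closes: "relationship to the study product will be presented by treatment group for AEs reported after randomization". Section 6.1 counts irritation, burning, ocular pain and itching among dry eye symptoms. Section 6.4 names instillation site discomfort, mild and transient, as the most common AE with reproxalap.

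**The concern.** The sole objective (Section 7.1) is to compare the safety and tolerability of two eye drops. The two passages bear on how a reaction to the drop itself is counted.

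The main point is the baseline. A subject scored in the few minutes after the drop reports any stinging at that moment. If that score is then used as the visit's baseline, the stinging is subtracted from every in-chamber score. The product that irritates more at instillation gets the larger subtraction. If the reaction then fades, that product can look better in the chamber than it is.

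The secondary point is AE recording. Stinging or burning after a drop can be read as an instillation reaction or as worse dry eye. On the second reading it is not an AE. It then gets no onset, severity or causality entry and does not reach the tables by treatment.

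**Working it through.** **Inputs.** Chamber entry = 0 minutes and drop = about -5 (Sections 8.1 and 10.1). In-chamber scores run every 5 (+2) minutes to 45 (Table 5.1-2). The plan gives no figure for drop reactions, so there is none to reproduce.

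**Windows for the Visit 2 and 3 pre-chamber score**

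| Source | Minutes from entry | Part after the drop |
|---|---|---|
| Section 11.3 | -5 - 15 = -20, to -5 | none |
| Synopsis | about -5 - 15 = -20 | none |
| Table 5.1-1 footnote 2, Table 5.1-2, Section 12.1.1 | -15 to 0 | -5 to 0, i.e. 5/15 = 33% |

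The Section 11.3 window and the entry-anchored window overlap from -15 to -5. Those 10 minutes all precede the drop. The synopsis time of about -20 lies nominally outside the entry-anchored window. A score taken between -5 and 0 meets the tables and Section 12.1.1 but breaches the synopsis and Section 11.3.

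**Effect on the change score, if each visit's own score is the baseline.** Let d be the difference between products in drop reaction at a post-drop baseline. Let p be the share of subjects scored after the drop, taken as equal for both products. Let r be the share of d still present at a given in-chamber score. All three are assumptions.

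- Pre-dose baseline: difference in change = d x r.
- Entry-anchored baseline: difference in change = d x r - p x d = d x (r - p).
- Shift = p x d, in favour of the product with the stronger reaction.

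| p | Shift, d = 1 point | Shift, d = 2 points |
|---|---|---|
| 0 | 0 | 0 |
| 0.10 | 0.10 | 0.20 |
| 1/3 (scores spread evenly over the window) | 0.33 | 0.67 |
| 1 (every score taken after the drop) | 1.00 | 2.00 |

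The entry-anchored wording allows the whole range from p = 0 to p = 1.

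**When the sign reverses.** This needs r < p. Assume exponential fading with half-life h and a baseline 2.5 minutes after the drop. The condition at t minutes after the drop is h < (t - 2.5)/log2(1/p). The first in-chamber score comes at t = 5 + 5 = 10:

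- p = 1/3: 7.5/1.585 = 4.7 minutes.
- p = 0.10: 7.5/3.322 = 2.3 minutes.
- p = 1: any fading reverses the sign.

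A reaction that persists (r = 1) leaves d x (1 - p), so it is attenuated but not reversed.

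**If Visit 1 is the common baseline B.** Within a subject who completes both treatment visits, (Y_A - B) - (Y_B - B) = Y_A - Y_B. The baseline cancels and the shift is 0.

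**AE channel.** With a pre-dose baseline, the first score after the drop comes at 10 to 12 minutes (5 + 5 to 5 + 7). Post-chamber visual acuity and slit-lamp examination come at 45 + 5 = 50 minutes or later; the pre-chamber ones precede the questionnaires (Table 5.1-1, footnote 3). In the visible text, AE recording is therefore the only planned record of the first 10 minutes. Sections 14.2, 17.2, 17.2.1 and 17.2.2 contain no sentence that brings a drop-caused dry eye symptom back within AE recording.

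**The case against.** **On the baseline.** No section asks for a score after the drop. Section 11.3 is the visit-specific procedure and it says pre-dose, as does the synopsis. A site can satisfy Section 11.3 and the tables together by scoring between -15 and -5, and then nothing is subtracted. If Visit 1 is the baseline, as its column heading may suggest, the term cancels. All of this stands. A reader might infer that the plan builds a bias into the change scores. The documents do not support that: they show a contradiction that permits a post-drop baseline, on one reading of an undefined term.

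**On AEs.** The exclusion does not mention instillation reactions. Section 17.2 defines an AE as any untoward occurrence associated with use of a drug. Section 12.2.7 has staff record whatever is observed, queried or volunteered after dosing, using non-leading questions. Section 6.4 itself classes instillation site discomfort as an AE, and Section 17.2.2 requires all serious events to be reported. A careful site would probably record a drop reaction. A reader might infer that drug reactions will be missing from the tables. The text shows only that they may be, because it leaves the choice to whoever classifies the complaint.

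**On scope.** Section 6.4 says acute drop comfort was characterised in two earlier trials, and the text that follows is redacted. The absence of an early post-drop score here is therefore not treated as a fault.

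**Conclusion.** The point holds as a contradiction to reconcile, with a secondary gap in the AE wording.

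For the baseline, 5 of the 15 entry-anchored minutes (33%) follow the drop. The consequence depends on each visit's own score being the baseline and on some subjects being scored in those minutes. If both are true, the product difference in change shifts by p x d. The documents give neither p nor d, so the tabulated values are illustrations and p = 1/3 is not a ceiling. The effect is zero if the site follows the synopsis and Section 11.3, or if Visit 1 is the common baseline.

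For AEs, an under-count of drop reactions is possible. Its size is unknown, because no reaction rate is given for either product under this rule.

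The trial is exploratory with no stated test (Section 14.1), so what is at risk is a descriptive comparison. That comparison is still what the trial delivers, and Section 13.1 allows the report into regulatory submissions. The wording should be corrected; the point does not call the design into question.

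**What to change.** 1. Reconcile footnote 2 of Table 5.1-1, Table 5.1-2, Section 12.1.1 and the Visit 1 bullet of Section 11.2 with the synopsis and Section 11.3, so that the pre-chamber score is always taken before instillation (saline or test product). Relabel time 0 in Table 5.1-2 as pre-dose.
2. State in Section 5.1.1, and in the matching synopsis endpoint, that each visit's own pre-instillation score is the baseline for that visit.
3. In Section 17.2.1, keep the exclusion for dry eye worsening not attributed to study product, both during washout and as the expected chamber response. Add that ocular complaints starting between instillation and chamber entry, or judged related to study product, are recorded as AEs and tabulated by product. Add also that a change in a 0-10 score alone is not an AE. Keeping the exclusion for washout avoids turning ordinary dry eye worsening into AEs in subjects who must stop their own drops.

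Cost: one protocol amendment with ethics-board handling (Sections 20.1 and 20.4). It adds no visit, assessment or staff. The downside is somewhat more mild ocular AEs recorded for both products.

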17.2.2 Reporting Serious Adverse Events

AEs and medical history will be coded and classified according to the MedDRA, and AEs will be reported with respect to severity, duration, relationship to study drug(s) and action taken. Concomitant medications will be categorized using the World Health Organization Drug Dictionary (the most updated version of the dictionary) at the start of the study.

All serious adverse experiences, whether deemed drug-related or not, will be reported to ProPharma Group preferably by email (or by telephone if email is not possible) immediately after the awareness by Investigator and in no case later than 24 hours, followed by a written report within 2 working days. The investigator is responsible for following all local regulations for the reporting of safety information, including the reporting of SAEs to their local IRB/Research Ethics Board (REB)/Independent Ethics Committee (IEC).

The investigator must promptly report to his or her local IRB/REB/IEC all unanticipated problems involving risks to subjects. This includes death from any cause and all serious adverse events reasonably or possibly associated with the use of the investigational product.

The Sponsor (PI) or their designee is responsible for appropriate reporting of relevant AEs, suspected unexpected serious adverse reactions (SUSARs) involving investigational product, to all regulatory authorities as per the below timeline:

- When neither fatal nor life-threatening, within 15 days after becoming aware of the information
- When fatal or life-threatening, immediately when possible and, in any event, within seven (7) days after becoming aware of the information
- Within eight (8) days after having informed Health Canada of the adverse drug reaction, submit a report that includes an assessment of the importance and implication of any findings

In addition, the Sponsor (PI) or designee will be responsible for the submission of safety letters (e.g., SUSARs) to the central IRB/REB/IEC and participating investigators of all SUSARs involving IP according to applicable regulations.

After termination of the clinical trial (determined as last subject, last visit), any unexpected safety issue that changes the risk-benefit analysis and is likely to have an impact on the subjects who have participated in it will be reported by the Sponsor (PI) as soon as possible to the competent authority (ies) concerned together with proposed actions.

17.2.3 Removal of Subjects from Study

Subjects will be advised that they are free to withdraw from the study at any time for any reason or, if necessary, the Investigator may withdraw a subject from the study to protect the health of that subject. A subject may also be withdrawn for not complying with study procedures. The clinical report will include all reasons for early withdrawals.

All subjects who receive at least one dose of either of the study products will be included in the safety analysis. If a subject terminates from the study early, all efforts will be made to complete all applicable safety procedures. In case of early termination, the Investigator will fully document the reason for early termination. Reasons for the early termination may include the following:

- Voluntary withdrawal by subject.
- Significant AE that led the Investigator or subject to withdraw for safety reasons.

- Non-compliance with protocol requirements (e.g., use of restricted medication, not following dosing procedures, failure to make scheduled study visits in a timely fashion).
- Pregnancy
- Participant enrolls in another clinical trial or is found to have previously enrolled in this clinical trial.
- Positive COVID-19 test result.

17.2.4 Termination of Study Due to Adverse Events

If, in the opinion of the Sponsor (PI), Regulatory authorities or the IRB, the incidence and severity of AE(s) outweighs the benefit of continuing the study, the study may be terminated.

18. ETHICS OF CONDUCT

This study will be conducted in compliance with the protocol and accordance with the appropriate guidelines and all applicable federal government codes, acts and regulations, the ethical principles that have their origins in the Declaration of Helsinki and all amendments, Good Clinical Practice (GCP) requirements, the International Council for Harmonisation of Technical Requirements for Pharmaceuticals for Human Use (ICH) guidance E6 (R2), and Tri-Council Policy Statement (Canada). Protocol and Informed Consent approval by the Ethics Board will be sought prior to the commencement of the study, and a copy of the Ethics attestation will be sent to the Sponsor (PI).

19. QUALITY CONTROL AND QUALITY ASSURANCE

Cliantha Research will implement and maintain quality control procedures to ensure that the study is conducted and that the data are generated, documented, and reported in compliance with the protocol, GCP and applicable regulatory documents.

- All participant data relating to the study will be recorded on electronic CRF unless transmitted to the Sponsor (PI) or designee electronically (e.g., laboratory data). The Investigator is responsible for verifying that data entries are accurate and correct by electronically signing the CRF.
- The Investigator must maintain accurate documentation (source data) that supports the information entered in the CRF.
- The Investigator must permit study-related monitoring, audits, IRB/IEC review, and regulatory agency inspections and provide direct/remote access to source data documents.
- Study monitors will perform ongoing source data verification to confirm that data entered into the CRF by authorized site personnel are accurate, complete, and verifiable from source documents; that the safety and rights of participants are being protected; and that the study is being conducted in accordance with the currently approved protocol, written SOPs, study-

specific plans and any other study agreements, ICH GCP, and all applicable regulatory requirements.

- Separate risk management plan will be developed prior to the start of the study in accordance with ICH E6 (R2).

19.1 Pandemic COVID-19 Response Plan

Regulatory authorities have recognized that the Coronavirus Disease 2019 (COVID-19) pandemic may impact the conduct of the clinical study. COVID-19 pandemic has created a lot of uncertainty in the current situation and has put the subject's safety, protocol compliance and data validity at high risk.

Due to the COVID-19 pandemic, challenges may arise for clinical study conduct, for example, quarantines of site personnel/study participants, travel limitations, interruptions to the supply chain for the IP(s), or other considerations if site personnel or study participants become infected with COVID-19. These challenges may lead to difficulties in meeting protocol-specified procedures, including administration or use of the investigational product, housing duration or adhering to protocol specified visits and laboratory/diagnostic testing.

To accommodate these challenges and mitigate safety risks associated with COVID-19, changes may be required from approved protocol which includes (but not limited to) conducting the study in multiple groups, change in study procedures timing, change in subject's housing duration; ambulatory visits, additional test or parameter may be performed to standard inclusion or exclusion criteria at the discretion of Investigator/designee, etc. The changes made to the procedure will prioritize the subject's safety and data validity and integrity. For any significant change, as per regulatory guidelines, a planned protocol deviation will be filled and notified to IRB and/or local regulatory (as applicable).

All participants will be pre-screened prior to enrolment into the study and evaluated for risk factors and symptoms of COVID-19 according to the most recent regional Public Health guidelines¹³ available at the time of pre-screening. The screening is conducted through telephone at the time of appointment confirmation and again when the subject arrives at the clinic for any visit.

Additional health checks, including body temperature or other vital sign monitoring, etc., may be performed during the study at the discretion of the Investigator/designee, even if not specified in the protocol. A subject who is tested positive to COVID-19 during the study will be withdrawn from the study. This subject and other subjects in close contact will be handled as per applicable local Public Health Guidelines.

As the science and regulations are continuously being adapted to the evolving information around the pandemic, additional measures apart from the ones mentioned here may be undertaken to ensure subject safety and appropriate study conduct. The IRB would be informed for their review and approval as applicable.

Risk Mitigation plan/Risk Evaluation and Mitigation strategy will be made to minimize the risk for COVID-19 exposure and to handle possible situations during the COVID-19 pandemic.

